9.1.2 Adverse Events

An adverse event is defined as any untoward medical occurrence in a clinical trial subject. The event does not necessarily have a causal relationship with study treatment. The investigator is responsible for ensuring that any adverse events observed by the investigator or reported by the subject are recorded in the subject's medical record.

The definition of adverse events includes worsening of a pre-existing medical condition. Worsening indicates that the pre-existing medical condition or underlying disease (eg diabetes, migraine headaches, gout) has increased in severity, frequency, and/or duration more than would be expected, and/or has an association with a significantly worse outcome than expected. A pre-existing condition that has not worsened more than anticipated (ie, more than usual fluctuation of disease) during the study or involves an intervention such as elective cosmetic surgery or a medical procedure while on study, is not considered an adverse event.

If the severity of an adverse event changes from the date of onset to the date of resolution, record as a single event with the worst severity on the Event CRF.

For situations when an adverse event or serious adverse event is due to DLBCL, report all known signs and symptoms. Death due to disease progression in the absence of signs and symptoms should be reported as the primary tumor type (eg, DLBCL).

Note: The term "disease progression" should not be used to describe the disease-related event or adverse event.

An adverse device effect is any adverse event related to the use of a medical device. Adverse device effects include adverse events resulting from insufficient or inadequate

instructions for use, adverse events resulting from any malfunction of the device, or adverse events resulting from use error or from intentional misuse of the device.

The investigator's clinical judgment is used to determine whether a subject is to be removed from treatment due to an adverse event. In the event a subject, or subject's legally acceptable representative requests to withdraw from protocol-required therapies or the study due to an adverse event, refer to [Section 8.1](#) for additional instructions on the procedures recommended for safe withdrawal from protocol-required therapies or the study.

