9.2.2 Adverse Events

9.2.2.1 Reporting Procedures for Adverse Events That do not Meet Serious Criteria

The investigator is responsible for ensuring that all adverse events observed by the investigator or reported by the subject that occur after first dose of blinatumomab through the safety follow-up visit are reported using the Event CRF.

The investigator must assign the following adverse event attributes:

- adverse event diagnosis or syndrome(s), if known (if not known, signs or symptoms)
- dates of onset and resolution (if resolved)
- severity (and/or toxicity per protocol)
- assessment of relatedness to investigational product(s), medical device(s) or other protocol-required therapies
- action taken.

The adverse event grading scale used will be the Common Terminology Criteria for Adverse Events (CTCAE) version 4.0. The grading scale used in this study is described in [Appendix A](#).

The investigator must assess whether the adverse event is possibly related to the investigational product(s), and/or other protocol-required therapies. This relationship is indicated by a “yes” or “no” response to the question: Is there a reasonable possibility that the event may have been caused by the investigational product(s), and/or other protocol-required therapies?

The investigator is responsible for reviewing laboratory test results and determining whether an abnormal value in an individual study subject represents a clinically significant change from the subject's baseline values. All grade 3 and grade 4 laboratory values should be recorded as adverse events. In addition, if signs or symptoms are associated with the laboratory abnormality, the signs/symptoms and the laboratory abnormality should all be recorded as adverse events. The laboratory abnormality and any signs/symptoms should be graded according to their own CTCAE criteria.

The investigator is expected to follow reported adverse events until stabilization or reversibility.

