9.2.2.2 Reporting Procedures for Serious Adverse Events

The investigator is responsible for ensuring that all serious adverse events observed by the investigator or reported by the subject that occur after signing of the informed consent through 30 days after the last dose of investigational product are recorded in the subject's medical record and are submitted to Amgen. Additionally blinatumomab-related serious adverse events that occur after the safety follow-up visit through the end of the long-term follow-up will be reported.

All serious adverse events must be submitted to Amgen within 24 hours following the investigator's knowledge of the event via the Event CRF.

If the electronic data capture (EDC) system is unavailable to the site staff to report the serious adverse event, the information is to be reported to Amgen via an electronic Serious Adverse Event Contingency Report Form within 24 hours of the investigator's knowledge of the event. See [Appendix B](#) for a sample of the Serious Adverse Event Worksheet /electronic Serious Adverse Event Contingency Report Form. For EDC studies where the first notification of a Serious Adverse Event is reported to Amgen via the eSerious Adverse Event Contingency Report Form, the data must be entered into the EDC system when the system is again available.

The investigator must assess whether the serious adverse event is possibly related to investigational product, medical device, and/or other protocol-required therapies. This relationship is indicated by a "yes" or "no" response to the question: Is there a reasonable possibility that the event may have been caused by the investigational product, medical device, and/or other protocol-required therapies? Relatedness means that there are facts or reasons to support a relationship between investigational product and the event.

The investigator is expected to follow reported serious adverse events until stabilization or reversibility.

New information relating to a previously reported serious adverse event must be submitted to Amgen. All new information for serious adverse events must be sent to Amgen within 24 hours following knowledge of the new information. If specifically requested, the investigator may need to provide additional follow-up information, such as discharge summaries, medical records, or extracts from the medical records.

Information provided about the serious adverse event must be consistent with that recorded on the Event CRF.

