10.4.4 Safety Endpoints

10.4.4.1 Adverse Events

The Medical Dictionary for Regulatory Activities will be used to code all adverse events to a system organ class and a preferred term. Adverse events of interest (EOI)

categories will be based on search strategies defined by Medical Coding. All adverse event tables will be summarized by treatment group. Treatment-emergent adverse events are events with an onset after the administration of the first dose of blinatumomab treatment.

The subject incidence of adverse events will be summarized for all treatment-emergent adverse events, serious adverse events, adverse events leading to withdrawal of protocol-specified therapy, and fatal adverse events.

Subject incidence of all treatment-emergent adverse events, serious adverse events, adverse events leading to withdrawal of blinatumomab, and fatal adverse events will be tabulated by system organ class and preferred term in descending order of frequency; similar summaries will be repeated for EOs. Time to onset and duration of selected EOs (infection and neurologic events) may also be summarized.

Any serious adverse event that occurs from enrolment through the day before the first dose of blinatumomab (during the run-in period) will be documented and summarised. This applies to all subjects who have been enrolled onto the study, regardless of whether they achieve the MRD-positive status required to start treatment with blinatumomab.

A summary of blinatumomab treatment-emergent adverse events will be tabulated by system organ class, preferred term, and worst grade.

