On and after study day 1: study day= (date - date of Study Day 1) + 1

Treatment-emergent adverse event (TEAE)

Adverse events (AEs) starting on or after first dose of protocol-specified therapy as determined by the flag indicating if the adverse event started prior to the first dose on the Adverse Events Summary CRF and up to and including 30 days after the end of protocol-specified therapy. This reporting window also applies to treatment-emergent serious adverse events (SAEs).

Treatment-emergent disease-related event

Events categorized as Disease-related Events (DREs) starting on or after first dose of blinatumomab as determined by the flag indicating if the event started prior to the first dose on the Events CRF and up to and including 30 days after the end of blinatumomab.

Disease Related Events

Subject incidence of disease related events and fatal disease related events in the blinatumomab treatment period (through the safety follow-up visit) will be tabulated by

system organ class and preferred term. Refer Protocol section 9.1.1 for more details on disease related events by their system organ class.

Triple hit

Triple hit is defined as the positive rearrangement of c-MYC, BCL2 and BCL6 as collected on the 'Disease-Specific Features on the DLBCL Disease History (COO)' eCRF page.

6. Analysis Sets

This study will define the following analysis sets for the purpose of statistical analysis: Full Analysis set, Primary analysis Set, Target Dose Analysis Set, Pre-treatment Analysis Set and Dose Limiting Toxicity (DLT) Analysis Set.

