9.6.2 Adverse Events

The Medical Dictionary for Regulatory Activities (MedDRA) version 21.1 or later will be used to code all events categorized as adverse events (AEs), disease-related events (DREs) to a system organ class and a preferred term. Treatment-emergent adverse events are events with an onset after the administration of the first dose of blinatumomab treatment through 30 days after the end of blinatumomab treatment. Adverse events of interest (EOI) categories will be based on search strategies defined by Medical Coding.

The subject incidence of adverse events will be summarized for all treatment-emergent adverse events, serious adverse events, adverse events leading to withdrawal of protocol-specified therapy, and fatal adverse events.

Subject incidence of all treatment-emergent adverse events, serious adverse events, adverse events leading to withdrawal of blinatumomab, leading to interruption of IP and fatal adverse events will be tabulated by system organ class and preferred term in descending order of frequency; similar summaries will be repeated for EOIs. Time to

onset and duration of selected EOIs (infection, neurologic events, and CRS) may also be summarized.

Any serious adverse event that occurs from enrolment through the day before the first dose of blinatumomab (during the run-in period) will be documented and summarized. This applies to all subjects who have been enrolled onto the study, regardless of whether they achieve the MRD-positive status required to start treatment with blinatumomab.

A summary of blinatumomab treatment-emergent adverse events will be tabulated by system organ class, preferred term, and worst grade.

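### Treatment-emergent status rests on onset alone, so a run-in SAE that worsens on blinatumomab can be left out of the treatment-emergent tables, and sites may handle it differently

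*Protocol*

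**What the plan says.** Three places define a treatment-emergent event:

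- Protocol 10.4.4.1: "Treatment-emergent adverse events are events with an onset after the administration of the first dose of blinatumomab treatment".
- SAP section 5 (Definitions): events starting on or after first dose, "as determined by the flag indicating if the adverse event started prior to the first dose on the Adverse Events Summary CRF", up to 30 days after the end of therapy. It adds that treatment-emergent SAEs follow the same window.
- SAP 9.6.2: onset after first dose "through 30 days after the end of blinatumomab treatment".

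None mentions an event that starts before first dose and worsens later.

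Protocol 9.1.2 governs the record itself. When severity changes between onset and resolution, the site is to "record as a single event with the worst severity on the Event CRF". The same section also says: "The definition of adverse events includes worsening of a pre-existing medical condition".

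The collection windows differ by seriousness. Protocol 9.2.2.2 covers SAEs "that occur after signing of the informed consent through 30 days after the last dose of investigational product". Protocol 9.2.2.1 covers non-serious events "that occur after first dose of blinatumomab through the safety follow-up visit are reported using the Event CRF".

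Protocol 10.4.4.1 and SAP 9.6.2 also plan a separate summary of SAEs occurring from enrolment to the day before first dose, and a table of treatment-emergent events by worst grade.

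**The concern.** The run-in can last up to 24 months, and SAEs are on record throughout it. If one is unresolved at first dose and deteriorates during infusion, the onset rule and the single-record rule together can leave a record with a pre-dose start and a severity reached on drug. The flag then takes it out of the treatment-emergent tables.

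The incidence, grade and severity of treatment-emergent events is a named secondary endpoint (protocol 10.1.1.2), so the definition determines an endpoint. For such a record the misclassification runs one way: worsening on drug leaves the blinatumomab tables. The study has a single arm, so no control group would reveal it. The subjects concerned would be those with serious events.

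**Working it through.** The plan states no figure for this point. The check is mainly a reading of the rules, followed by a simple sizing.

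**Tracing one record.** Take a hypothetical SAE with onset after enrolment, grade 2 and unresolved at first dose, reaching grade 4 during infusion.

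1. It is entered during the run-in, because SAE recording starts at consent (protocol 9.2.2.2).
2. On worsening, the single-record rule (protocol 9.1.2) gives one record with a pre-dose onset and worst severity 4.
3. The SAP section 5 flag reads as started before first dose, so the event is not treatment-emergent.
4. It is therefore absent from the all-treatment-emergent table and from the worst-grade table, which is limited to treatment-emergent events.
5. The serious and fatal tables are less certain. Protocol 10.4.4.1 and SAP 9.6.2 list serious and fatal events beside treatment-emergent events without attaching that label to each. SAP section 5 implies the restriction for SAEs.
6. The event still appears in the run-in SAE summary. Had its onset fallen between consent and enrolment, it would be outside that summary too, since the summary starts at enrolment.

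**The competing clause.** If the site instead treats the open SAE as a pre-existing condition under 9.1.2, the worsening is a new adverse event with post-dose onset, and it is counted. The examples given there are background illnesses (diabetes, migraine, gout), and medical history is collected only up to consent (protocol 7.3.3). This makes the single-record rule the closer fit, but the section does not say which rule governs.

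**Sizing.** The denominator is 30, the Primary Analysis Set (protocol 10.1.2.2), which SAP 6.6 uses for safety at the primary analysis. The number of affected subjects is an assumption, 0 to 2, because the documents give no rate. The loss in a row is at most (affected subjects)/30:

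- 0/30 = 0 points
- 1/30 = 3.3 points
- 2/30 = 6.7 points

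Exact (Clopper-Pearson) 95% intervals were used for illustration. The method reproduces the table in protocol 10.2, for example 8/30 gives 12.3 to 45.9% and 9/30 gives 14.7 to 49.4%. Suppose the only events in a row were the omitted ones:

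- Row as shown: 0/30 = 0%, interval 0 to 11.6%
- True count 1/30 = 3.3%, interval 0.1 to 17.2%
- True count 2/30 = 6.7%, interval 0.8 to 22.1%

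The tables report subject incidence. A subject who already has another event in the same row is counted anyway, and the loss in that row is then nil.

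**The case against.** The strongest reply is that 9.1.2 already covers the case. It does not confine pre-existing to conditions present before consent, and non-serious adverse events are collected only from first dose, so an SAE open at that point can be read as pre-existing and its worsening as a new event. This stands to the extent that omission is not certain. It does not remove the problem, because two sites following the same section could classify identical cases differently.

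The second reply is that the case is rare. Only SAEs can be affected, since non-serious run-in events are not collected. Part 2 eligibility requires adequate organ function within 7 days before assignment, no active infection needing systemic therapy, and no change in the Part 1 criteria, which themselves exclude clinically significant disorders judged to pose a risk. This stands too. Still, Part 2 does not require earlier SAEs to have resolved, and its limits (ANC of at least 1.0 and platelets of at least 75 × 10⁹/L) admit an improving but unresolved event.

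Third, other outputs capture on-drug deterioration. DLTs depend on grade and relatedness during cycle 1, not on the onset flag (protocol 6.2.2). The Data Review Team sees adverse events and DLTs in all subjects. Deaths after first dose count in OS and PFS. Laboratory worsening shows in the shift tables. All of this is correct, but the shift tables cover selected laboratory parameters only, and none of these outputs replaces the tables for the secondary endpoint.

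A reader might also infer that the run-in SAE summary will display a grade reached on drug. The documents do not support that: both say only that these SAEs will be documented and summarised, and neither plans a grade display.

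**Conclusion.** The point holds as a gap in the definition with an ambiguity in recording. A run-in SAE that worsens on blinatumomab can be omitted from the treatment-emergent and worst-grade tables. Omission from the serious and fatal tables depends on whether these are limited to treatment-emergent events.

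Two stronger readings are tempting and go too far. One is that every such event is necessarily left out: the clause on pre-existing conditions allows a site to open a new event. The other is that on-drug deaths are certainly missing from the fatal table: that table is not expressly labelled treatment-emergent.

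The effect is at most 3.3 percentage points per affected subject in 30, on an assumed 0 to 2 subjects; it may be zero. The stopping rule and the survival endpoints do not depend on it. CRF completion instructions are separate documents, so any handling there cannot be seen. The change is still worth making because any omission favours the drug and the wording is easily repaired.

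**What to change.** - **Definition (protocol 10.4.4.1, SAP sections 5 and 9.6.2):** treatment-emergent means onset, or increase in grade, or fatal outcome, on or after first dose through 30 days after the last dose, counted at the worst grade after first dose. This also settles the present difference between onset after first dose (protocol 10.4.4.1, SAP 9.6.2) and on or after it (SAP section 5).
- **Recording (protocol 9.1.2 or the CRF completion instructions):** an event ongoing at first dose that worsens afterwards is entered as a new event dated at the worsening, as a stated exception to the single-record rule.
- **Run-in SAE summary:** if it shows grade, use the worst grade before first dose.

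The cost is small wording changes in both documents and one CRF completion instruction, with no new visit. Protocol amendments need IRB/IEC approval (protocol 12.1), so the protocol wording is best carried in the next amendment.

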10.4.4.2 Disease Related Events

Subject incidence of disease related events and fatal disease related events in the blinatumomab treatment period (through the safety follow-up visit) will be tabulated by system organ class and preferred term.

10.4.4.3 Laboratory Test Results

Shift tables between the worst post-baseline and baseline grades for selected laboratory parameters will be provided. The analyses of selected safety laboratory parameters including immunoglobulins, platelets, and liver parameters will include summary statistics over time.

10.4.4.4 Vital Signs

The number and percentage of subjects with abnormal changes in systolic blood pressure, diastolic blood pressure and heart rate will be summarized.

10.4.4.5 Electrocardiogram

The ECG measurements from this clinical study were performed as per standard of care for routine safety monitoring, rather than for purposes of assessment of potential QTc effect. Since these evaluations may not necessarily be performed under the rigorous conditions expected to lead to meaningful evaluation of QTc data; summaries and statistical analyses of ECG measurements are not planned, and these data would not be expected to be useful for meta-analysis with data from other trials.

10.4.4.6 Antibody Formation

The incidence and percentage of subjects who develop anti-blinatumomab antibodies (binding and if positive, neutralizing) at any time may be tabulated.

10.4.4.7 Exposure to Investigational Product

Descriptive statistics will be produced to describe the exposure to blinatumomab for subjects in the Full Analysis Set. The number of days on IP and the proportion of subjects receiving each dose level will be summarized. In addition, the duration of therapy, the relative treatment duration, the cumulative dose, and the percent of intended dose will be summarized. The number and percent of subjects with dose modifications (eg, dose changes, dose interruptions) and reason for modification will be summarized.

10.4.4.8 Exposure to Concomitant Medication

The number and proportion of subjects receiving concomitant medications from enrolment through the day before the first dose of blinatumomab (run-in period) and from day 1 through safety follow-up will be summarized by preferred term as coded by the World Health Organization Drug dictionary by Full Analysis Sets. In addition, the number and proportion of subjects receiving anticancer therapies during long term follow-up will be summarized by World Health Organization Drug dictionary preferred term in the Full Analysis Set.

11. REGULATORY OBLIGATIONS

11.1 Informed Consent

An initial sample informed consent form is provided for the investigator to prepare the informed consent document to be used at his or her site. Updates to the template are to be communicated formally in writing from the Amgen Clinical Manager to the investigator. The written informed consent form is to be prepared in the language(s) of the potential patient population.

Before a subject's participation in the clinical study, the investigator is responsible for obtaining written informed consent from the subject or legally acceptable representative after adequate explanation of the aims, methods, anticipated benefits, and potential hazards of the study and before any protocol-specific screening procedures or any investigational product(s) is/are administered. A legally acceptable representative is an individual or other body authorized under applicable law to consent, on behalf of a prospective subject, to the subject's participation in the clinical study.

The investigator is also responsible for asking the subject if the subject has a primary care physician and if the subject agrees to have his/her primary care physician informed of the subject's participation in the clinical study. If the subject agrees to such notification, the investigator is to inform the subject's primary care physician of the subject's participation in the clinical study. If the subject does not have a primary care physician and the investigator will be acting in that capacity, the investigator is to document such in the subject's medical record.

The acquisition of informed consent and the subject's agreement or refusal of his/her notification of the primary care physician is to be documented in the subject's medical records, and the informed consent form is to be signed and personally dated by the subject or a legally acceptable representative and by the person who conducted the informed consent discussion. The original signed informed consent form is to be retained in accordance with institutional policy, and a copy of the signed consent form is to be provided to the subject or legally acceptable representative.

If a potential subject is illiterate or visually impaired and does not have a legally acceptable representative, the investigator must provide an impartial witness to read the informed consent form to the subject and must allow for questions. Thereafter, both the subject and the witness must sign the informed consent form to attest that informed consent was freely given and understood.

